11.3 Secondary Objectives Analysis

Serum anti-RSV NAb titer

Secondary immunogenicity endpoints are:

1. GMT of the serum anti-RSV NAb titer at Day 1 (baseline), Day 29 (28 days after the first dose), and Day 181 (six months after the first dose).
2. Proportion of subjects with a ≥ 4 -fold increase in serum anti-RSV NAb titer from Day 1 (baseline) to all other time points (Day 29 [28 days after the first dose] and Day 181 [six months after the first dose]).
3. Proportion of subjects at Day 29 (28 days after the first dose), Day 57 (28 days after the second dose), and Day 181 (six months after the first dose) who achieve serum anti-RSV NAb titers greater than the 3rd quartile of the serum anti-RSV NAb titers overall distribution at Day 1 (baseline).
4. Reverse cumulative distribution of serum anti-RSV NAb titers at Day 1 (baseline), Day 29 (28 days after the first dose), Day 57 (28 days after the second dose), and Day 181 (six months after the first dose).

The same statistical model as the one used for the primary objectives will be applied to evaluate the serum neutralizing antibody response at Day 1, Day 29 and Day 181. No test for interaction will be conducted for the GMT analyses.

Proportions of subjects with a ≥ 4 -fold increase in serum anti-RSV NAb titer from baseline will also be presented for each treatment group within each cohort together with their two-sided 95% Clopper-Pearson CIs. Additionally, the proportions of subjects whose serum anti-RSV NAb titer at Day 29, Day 57 and Day 181 greater than the third quartile (75-th percentile) of the serum anti-RSV NAb titer at Day 1 for all subjects combined will be presented for each treatment group within each cohort, together with their two-sided 95% CIs.

Reverse Cumulative Distribution Functions (RCDFs) will be produced.

Serum total binding antibody responses

Secondary immunogenicity endpoints are:

1. GMT of the serum total binding antibody to each of the RSV proteins F, G, and N at Day 1 (baseline), Day 29 (28 days after the first dose), Day 57 (28 days after the second dose), and Day 181 (six months after the first dose).
2. Proportion of subjects with a ≥ 4 -fold increase in serum total binding antibody titers to each of the RSV proteins F, G, and N from Day 1 (baseline) to all time points (Day 29 [28 days after the first dose], Day 57 [28 days after the second dose], and Day 181 [six months after the first dose]).
3. Proportion of subjects at Days 29 (28 days after the first dose), Day 57 (28 days after the second dose), and Day 181 (six months after the first dose) who achieve serum total binding antibody titers to each of the RSV proteins F, G, and N greater than the 3rd quartile of serum total binding antibody titers to RSV protein F at Day 1 (baseline).
4. Reverse cumulative distribution of serum total binding antibody to each of the RSV proteins F, G, and N at Day 1 (baseline), Day 29 (28 days after the first dose), Day 57 (28 days after the second dose), and Day 181 (six months after the first dose).

Analyses of the serum total binding antibody responses to each of the RSV proteins, F, G, and N will use the same primary ANCOVA model as for the primary objective. Similarly, the proportions of subjects with a ≥ 4 -fold increase in serum total binding antibody titers will be analyzed in the same manner as the anti-RSV NAb titers. Additionally, the third quartile of the serum total binding antibody to each of the RSV proteins at Day 1 for all subject combined will be determined; and, the proportions of

subjects with a post-vaccination titer greater than or equal to that value will be analyzed in the same manner as the 4-fold increase analyses.

Ratio of serum NAb titer to serum total binding antibody titers

1. Ratio of RSV F subunit serum neutralizing antibody (NAb) titer to each of the RSV F subunit serum total binding antibody titers to RSV proteins F, G, and N at Day 1 (baseline), Day 29 (28 days after the first dose), Day 57 (28 days after the second dose), and Day 181 (six months after the first dose).

Analyses of the ratio of serum NAb titer to serum total binding antibody titer to each of the RSV proteins (F, G, and N) will use the same primary ANCOVA model as for the primary objective with the serum NAb titer at Day 1 as the covariate.

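### SAP section 11.3 gives two conflicting rules for the third-quartile binding-antibody endpoint: the cut-off differs for G and N, and the inequality differs for all three proteins

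*SAP*

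**What the plan says.** The text at issue is in the last of the three SAP versions in the file, section 11.3, under serum total binding antibody responses.

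- **Endpoint list, item 3.** The endpoint is the proportion of subjects at Days 29, 57 and 181 "who achieve serum total binding antibody titers to each of the RSV proteins F, G, and N greater than the 3rd quartile". The quartile is then named as that of one protein only: "greater than the 3rd quartile of serum total binding antibody titers to RSV protein F at Day 1 (baseline".
- **Analysis paragraph after item 4.** Here "the third quartile of the serum total binding antibody to each of the RSV proteins at Day 1 for all subject combined will be determined". What is then counted is "subjects with a post-vaccination titer greater than or equal to that value".
- **Parallel neutralizing-antibody (NAb) endpoint, same section.** The definition reads "greater than the 3rd quartile of the serum anti-RSV NAb titers overall distribution at Day 1 (baseline" and its analysis text reads "greater than the third quartile (75-th percentile) of the serum anti-RSV NAb titer at Day 1 for all subjects combined". The two agree: own baseline distribution, strict inequality, all subjects pooled.

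Section 8.7 sets values below the limit of quantification (1:100) to 1:50. Section 8.4 says tests are descriptive only.

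**The concern.** One endpoint has two definitions, and a programmer cannot follow both. For G and N, item 3 asks whether an anti-G or anti-N titre exceeds a quartile of anti-F titres, whereas the analysis paragraph asks whether it reaches the quartile of its own baseline distribution. For F the cut-off is the same and only the treatment of ties differs.

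At stake are the reported proportions for G and N at three time points. The SAP does not describe the binding assays or say that F, G and N titres can be compared on one scale. If their distributions differ, the F cut-off falls at an arbitrary point of the G or N distribution, and the proportion can be close to 0% or 100% in every group. Section 16 has a second programmer review the secondary immunogenicity programs. Two programmers could each follow the SAP and obtain different results, and a choice made after unblinding would be post hoc.

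**Working it through.** The SAP gives no expected proportion for this endpoint, so there is no planned figure to reproduce.

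**1. The two rules side by side**

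| Protein | Item 3 | Analysis paragraph | Conflict |
|---|---|---|---|
| F | > Q3 of F | ≥ Q3 of F | inequality |
| G | > Q3 of F | ≥ Q3 of G | cut-off and inequality |
| N | > Q3 of F | ≥ Q3 of N | cut-off and inequality |

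**2. Effect of the cut-off**

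The assumptions, none taken from the SAP, are normal log10 titres, the same SD s for F and for G or N, a G or N median equal to f times the F median, and no response to vaccination. Little G or N response is the relevant case. The vaccine is an F glycoprotein (section 1), and section 7.4 removes subjects with a 4-fold or greater rise in N or G from the per-protocol set.

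Share above the F cut-off = 1 − Φ(0.6745 − log10(f)/s).

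Example with f = 0.5, s = 0.4: 1 − Φ(0.6745 + 0.301/0.4) = 1 − Φ(1.427) = 7.7%.

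| G or N median relative to F | s = 0.3 | s = 0.4 | s = 0.6 |
|---|---|---|---|
| 4-fold lower | 0.4% | 1.5% | 4.7% |
| 2-fold lower | 4.7% | 7.7% | 12.0% |
| equal | 25.0% | 25.0% | 25.0% |
| 2-fold higher | 62.9% | 53.1% | 43.1% |
| 4-fold higher | 90.9% | 79.7% | 62.9% |

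With the protein's own cut-off the share is 25% in every row. In a group of 24 (section 4.1) that is 6 subjects, with a 95% Clopper-Pearson interval of 9.8 to 46.7%. At s = 0.4 the F cut-off would give about 24 × 0.077 = 1.8 subjects (2-fold lower) or 24 × 0.531 = 12.7 (2-fold higher).

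**3. Effect on a comparison between groups**

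A 2-fold rise moves a group one step up the table, from 4-fold lower to 2-fold lower or from equal to 2-fold higher. At s = 0.4, the own cut-off shows it as 25.0% to 53.1%, a gain of 28.1 points. If G or N run 4-fold below F, the F cut-off shows it as 1.5% to 7.7%, a gain of 6.2 points. The contrast shrinks but keeps its sign.

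**4. Effect of the inequality**

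- Ties at the cut-off count under ≥ and not under >. Suppose titres are recorded in 2-fold steps from 1:100, with an underlying median of 1:800 and no response (assumptions). At s = 0.4 the quartile is 1:800. The share at or above it is 50%, and the share strictly above it is 1 − Φ(0.301/0.4) = 22.6%. This applies to F as well.
- If at least about 75% of Day 1 values for an antigen were below the limit of quantification, its quartile would be 1:50. Every later value is at least 1:50, so ≥ would count 100% of subjects. This step needs no distributional assumption.

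**The case against.** Much can be said for treating this lightly. The endpoint is secondary, testing is descriptive, and section 11.2 produces no group differences for the 4-fold proportions whose manner this analysis follows. The cut-off conflict touches only the two antigens that are not in the vaccine. The natural-infection rule in section 7.4 uses a 4-fold rise, not this quartile. Geometric mean titres, 4-fold proportions and reverse cumulative distributions are planned for each protein, so the titre distributions will be reported whichever cut-off is used. The analysis paragraph already contains the sensible cut-off, and item 3 is probably a drafting slip. All of this stands and limits the consequence. It does not settle which rule governs, because the SAP gives no order of precedence.

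A reader might infer that F, G and N titres have no common scale and that F's quartile is meaningless for G and N. The document does not support that: it is silent on the assays and gives a single limit of 1:100. What can be said is that a common scale is not established. A reader might also infer that the endpoint would measure assay scale instead of response. That goes too far, since every group, including the concurrent randomized placebo group, faces the same cut-off. The risk is lost sensitivity at floor or ceiling. Nor does the SAP state 25% as an intended reference share; that figure follows from using a protein's own quartile. Finally, nothing in the SAP suggests that three quarters of baseline values fall below the limit of quantification, so the 100% result is conditional.

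**Conclusion.** The point holds as an internal inconsistency within section 11.3. For G and N the cut-off and the inequality both conflict; for F only the inequality does. It is not a difference from superseded text, because the two earlier SAP versions in the file do not define this endpoint.

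The size is conditional. With no response, equal SDs of 0.3 to 0.6 and a 2-fold offset in either direction, the F cut-off gives about 5 to 12% or 43 to 63% where the own cut-off gives 25%. If the three baseline distributions coincided, the cut-off conflict would be harmless. The effect of the inequality depends on how often titres tie at the quartile. The primary endpoints and the sample size are untouched. It should be corrected before analysis, but it does not threaten the trial's main conclusions.

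**What to change.** Use the same wording in item 3 of the binding-antibody endpoints and in the analysis paragraph: *greater than the third quartile of the Day 1 titre to the same protein, all subjects combined*. This matches the NAb endpoint in the same section, gives each protein a cut-off from its own distribution, and avoids counting ties at 1:50 as exceedances. The essential requirement is a single cut-off rule and a single inequality in both places.

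The cost is two sentences in the SAP, agreed before unblinding. The protocol is not at hand; if it carries the item 3 wording, the SAP should record the change so that the two documents agree.

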11.2 Primary Objectives Analysis

Primary Objective:

To evaluate the serum neutralizing antibody (NAb) response to the RSV F subunit vaccine or placebo at Day 57 (28 days after the second dose).

Primary Immunogenicity Endpoints:

- Geometric mean titer (GMT) of the serum anti-RSV neutralizing antibody (NAb) titer at Day 57 (28 days after the second dose).
- Proportion of subjects with a ≥ 4 -fold increase in serum anti-RSV NAb titer from Day 1 (baseline) to Day 57 (28 days after the second dose).

It is assumed that log-transformed antibody titers are normally distributed; therefore values will be logarithmically transformed (base10) and all statistical analyses on antibody levels will be performed on the logarithmic scale.

Statistical models:

GMTs:

For each treatment group, GMTs of the serum anti-RSV NAb along with their associated 95% CIs will be computed by exponentiation of the corresponding log-transformed means and 95% CIs. In addition, median, minimum and maximum values will be calculated for each vaccine group at each time-point.

Adjusted GMTs for adjuvant groups within each cohort (dosage level) separately will come from an ANCOVA model including fixed factor for adjuvant and covariate adjustment for baseline value.

The following SAS® code will be used for the ANCOVA model:

```
PROC GLM data = dataset;  
BY cohort antigen visitnum;  
class adjuvant;  
model logtiter_post = adjuvant logtiter_pre;  
LSMEANS adjuvant / stderr cl OUT=LSMEANS;
```

RUN;

Adjusted GMTs for dosage groups within each adjuvant separately will come from an ANCOVA model including fixed factor for dosage and covariate adjustment for baseline value.

The following SAS® code will be used for the ANCOVA model:

```
PROC GLM data = dataset;  
BY adjuvant antigen visitnum;  
class dosage;  
model logtiter_post = dosage logtiter_pre;  
LSMEANS dosage / stderr cl OUT=LSMEANS;  
RUN;
```

The factorial design of the study allows fitting a statistical model able to evaluate the impact of each factor in explaining the antibody response; the following analysis of covariance (ANCOVA) model will be utilized:

$$Y_{ijk} = \mu + \alpha_i + \beta_j + \gamma X_{ijk} + t_{ijk}$$

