where Y_{ijk} represents the log-transformed (base 10) titer of the k^{th} subject in the dosage group i ($i= 45\mu\text{g}, 90\mu\text{g}$ or $135\mu\text{g}$) and adjuvant group j ($j=$ no adjuvant, aluminum or MF59); μ is the overall mean; α_i is the main effect of dosage i ; β_j is the main effect of adjuvant j , γ is a parameter included to adjust for continuous covariate X_{ijk} representing baseline titer; t_{ijk} are error terms normally distributed with mean zero and variance σ^2 .

The following SAS® code will be used for the ANCOVA model:

```
PROC GLM data = dataset;  
BY antigen visitnum;  
class dosage adjuvant;  
model logtiter_post = dosage adjuvant logtiter_pre;  
LSMEANS dosage adjuvant / stderr tdiff cl pdiff OUT=LSMEANS;  
ESTIMATE "dose 45 vs dose 90" dose 1 -1 0;  
ESTIMATE "dose 90 vs dose 135" dose 0 1 -1;  
ESTIMATE "dose 45 vs dose 135" dose 1 0 -1;  
ESTIMATE "no adj vs alum" adjuvant 1 -1 0;  
ESTIMATE "alum vs MF59" adjuvant 0 1 -1;  
ESTIMATE "no adj vs MF59" adjuvant 1 0 -1;  
RUN;
```

where `logtiter_post` represents the log-transformed antibody value of the immunogenicity variable at a given post baseline timepoint, `dosage` indicates the amount of vaccine content, `adjuvant` the type of adjuvant (i.e none, aluminum hydroxide or

MF59), `logtiter_pre` the log-transformed antibody baseline value of the immunogenicity variable.

Placebo will not be considered in this analysis.

Analysis of interaction:

To test for a possible effect modifier, a dosage by adjuvant interaction will be added to the previous ANCOVA model. With an overall p-value smaller than 0.05, further investigations will be conducted to better understand the degree of the interaction. Additional examinations will include point estimates and 95% CIs for the different levels (e.g. low dosage by no adjuvant, low dosage by alum and so forth) of the factors under study.

4-fold increase:

Proportions of subjects with a ≥ 4 -fold increase in serum anti-RSV NAb titer from baseline will be presented, for each treatment group within each cohort, together with their two-sided 95% Clopper-Pearson CIs (Clopper, 1934). Group differences will not be produced.

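### The secondary ANCOVA is applied to Day 1 titers, where response and covariate are the same number, and the NAb/binding ratio is adjusted for Day 1 NAb but not for Day 1 binding titer

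*SAP*

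**What the plan says.** The file holds three successive SAP versions; this point concerns the last one.

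- **Primary model (section 11.2).** The within-cohort code is "model logtiter_post = adjuvant logtiter_pre" and the factorial code is "model logtiter_post = dosage adjuvant logtiter_pre". The response "represents the log-transformed antibody value of the immunogenicity variable at a given post baseline timepoint". The covariate is "the log-transformed antibody baseline value of the immunogenicity variable".
- **Secondary NAb analysis (section 11.3).** The same model "will be applied to evaluate the serum neutralizing antibody response at Day 1, Day 29 and Day 181".
- **Binding antibody to F, G and N (section 11.3).** The analyses "will use the same primary ANCOVA model as for the primary objective". The sentence names no visits, but the GMT endpoints listed above it include Day 1.
- **Ratio of NAb to binding antibody (section 11.3).** The endpoint is listed at Days 1, 29, 57 and 181. Its analysis uses the "same primary ANCOVA model as for the primary objective with the serum NAb titer at Day 1 as the covariate".
- **Other baseline output.** Section 11.2 also plans unadjusted NAb GMTs with 95% CIs by group, and the median, minimum and maximum by group and time point. Section 11.3 plans reverse cumulative distributions that include Day 1 for NAb and for binding antibody.

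**The concern.** There are two separate faults.

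**Day 1 as a response.** Section 11.2 allows only post-baseline values on the left of the model, and section 11.3 then names Day 1. With the Day 1 titer on both sides, the model has nothing left to estimate. Section 8.1 says that summary tables will show adjusted GMTs, so the empty result could be tabulated as if it were an estimate.

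**The ratio's covariate.** On the log scale the ratio is log10 NAb minus log10 binding titer. Section 11.2 would adjust it for its own baseline, but section 11.3 adjusts for the baseline numerator only. Two things are at stake for secondary objectives 3 and 4. One is precision, with about 24 subjects per group. The other is the dosage contrasts: cohorts are enrolled one after another, so randomisation does not balance baseline binding titer between dosages. If the ratio model is also run at Day 1, its covariate is the numerator of its own response.

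**Working it through.** The SAP gives no figure to reproduce here. Part 1 is algebra and needs no assumption. Parts 2 and 3 need correlations that the SAP does not give, so the values are assumed and a range is shown.

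**1. Day 1 titer regressed on itself.** Write x for the Day 1 log10 titer. The model is x = a_g + b·x + error. The choice b = 1 and all a_g = 0 gives a residual sum of squares of exactly 0, so it is the least-squares fit. Each adjusted mean is a_g + b·x̄ = x̄, the overall mean in that run, with standard error 0.

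A check on simulated log10 titers, 4 groups of 24 with deliberately unequal baselines:

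| Group | Raw GMT | Adjusted GMT (95% CI) |
|---|---|---|
| No adjuvant | 557.7 | 530.05 (530.05 to 530.05) |
| Aluminum | 499.8 | 530.05 (530.05 to 530.05) |
| MF59 | 381.0 | 530.05 (530.05 to 530.05) |
| Placebo | 743.3 | 530.05 (530.05 to 530.05) |

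The slope was 1, all group effects 0 and the residual SD about 1e-15. The factorial model (9 groups of 24) also gave dosage and adjuvant effects of 0, with residual variance about 4e-30.

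**2. Precision of the ratio after baseline.** Take unit SDs, NAb-binding correlation k at each visit, pre/post correlation r for both assays, and correlation c between Day 1 of one assay and the later value of the other. The log ratio has variance 2(1−k). Its residual variance is:

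- given Day 1 NAb: 2(1−k) − (r−c)²
- given the Day 1 ratio: 2(1−k) − 2(r−c)²/(1−k). In this symmetric case, both Day 1 titers give the same value.

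| k | r | c | Day 1 NAb | Both Day 1 titers | Variance ratio |
|---|---|---|---|---|---|
| 0.3 | 0.5 | 0.4 | 1.4 − 0.01 = 1.39 | 1.4 − 0.029 = 1.371 | 1.01 |
| 0.3 | 0.5 | 0.1 | 1.4 − 0.16 = 1.24 | 1.4 − 0.457 = 0.943 | 1.32 |
| 0.3 | 0.7 | 0.4 | 1.4 − 0.09 = 1.31 | 1.4 − 0.257 = 1.143 | 1.15 |
| 0.3 | 0.7 | 0.1 | 1.4 − 0.36 = 1.04 | 1.4 − 1.029 = 0.371 | 2.80 |

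The unstated cross-correlation c drives the result as much as r does. A simulation with two arms of 24, SD 0.4 log10, k from 0.3 to 0.7, r from 0.4 to 0.8 and c = r·k gave standard errors 1.06 to 1.59 times those with the Day 1 ratio, a variance ratio of about 1.06² = 1.12 to 1.59² = 2.53. The extra covariate cost little. For k = 0.3 and r = 0.4, the SE was 0.133 with Day 1 NAb, 0.125 with the Day 1 ratio and 0.127 with both titers.

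The Day 1 ratio is not always the better single covariate. Take pre/post correlation 0.7 for NAb but 0.1 for binding, with k = 0.3:

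- Both cross-correlations 0.2. The covariance of the later log ratio with Day 1 NAb is 0.7 − 0.2 = 0.5, and with Day 1 binding 0.2 − 0.1 = 0.1. Residual variance is 1.4 − 0.25 = 1.15 given Day 1 NAb, 1.4 − 0.4²/1.4 = 1.286 given the Day 1 ratio, and 1.4 − (0.25 − 0.03 + 0.01)/0.91 = 1.147 given both. Day 1 NAb has 1.15/1.286 = 0.89 of the variance with the Day 1 ratio, and 1.15/1.147 = 1.00 of that with both.
- Cross-correlations 0.21 (Day 1 NAb with later binding) and 0.03 (Day 1 binding with later NAb). The covariances are 0.49 and −0.07. Residual variance is 1.4 − 0.240 = 1.160 given Day 1 NAb and 1.4 − 0.56²/1.4 = 1.176 given the Day 1 ratio, a quotient of 0.99.

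**3. Baseline binding difference in a non-randomised contrast.** Assume no true effect, a binding difference of 0.15 log10 at Day 1 (1.41-fold) and the structure c = r·k. Adjusting for NAb alone leaves a difference of −r × 0.15 in the log ratio: −0.06 for r = 0.4 and −0.12 for r = 0.8. That is a ratio of ratios of 10^−0.06 = 0.87 to 10^−0.12 = 0.76 instead of 1. The simulation gave 0.76 to 0.88. With both Day 1 titers in the model, the estimates stayed within 0.003 log10 of zero.

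**The case against.** The Day 1 wording may be no more than a loose visit list. Section 11.2 limits the model to post-baseline values, and a fit with zero residual variance would be noticed at the first run. For binding antibody, the model sentence names no day. This stands as a limit on the harm, but not as a defence of the text: for NAb, Day 1 is named, and the two sections cannot both be followed.

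A reader might infer that the plan would hide a real baseline imbalance. It would not: the unadjusted NAb GMTs, the medians and ranges by time point, and the Day 1 distributions would all show it.

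A reader might also infer that the ratio comparison is invalid. Within a cohort, subjects are randomised 1:1:1:1, so any prespecified baseline covariate gives a valid comparison. Day 1 NAb is then an efficiency choice, on secondary endpoints of a Phase 1 study whose tests are descriptive (section 8.4).

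Nor do the documents support a fixed large loss of precision, or a claim that the Day 1 ratio is always the better covariate. No correlations are given, and the order can reverse. In the population, both Day 1 titers together cannot give a higher residual variance than either alternative, because each is a special case of that model.

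Finally, the 1.41-fold imbalance is hypothetical, and sequential cohorts confound dosage contrasts whatever the covariate. Adjusting for baseline binding removes one route only.

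**Conclusion.** The Day 1 instruction is wrong as written. For NAb this follows from the text and from algebra: identical adjusted GMTs with zero-width intervals. For binding titers it follows only if the model is run on every listed endpoint day. The damage is meaningless adjusted output, not a lost baseline.

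The ratio covariate is inconsistent with the SAP's own definition in section 11.2. It is valid within cohorts, but it leaves baseline binding titer unadjusted. Under the assumed correlations, residual variance runs from about 1.0 to 2.8 times that with both Day 1 titers; the true size is unknown. In dosage contrasts, a baseline binding difference passes partly into the estimate: 0.76 to 0.88 instead of 1 for an assumed 1.41-fold difference. The change is worth making because it is cheap, not because a large loss has been shown.

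**What to change.** In section 11.3:

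1. Restrict the ANCOVA to Days 29, 57 and 181 for NAb, binding antibody and the ratio. Remove Day 1 from the sentence on the NAb model.
2. Report Day 1 titers and Day 1 ratios as unadjusted geometric means with 95% CIs. Section 8.9 describes GMTs as back-transformed least squares means, so it should say that Day 1 uses the plain formula in section 8.7.
3. For the ratio after baseline, state that the response is the log10 ratio, and include both Day 1 log10 NAb and Day 1 log10 binding titer to the same protein (F, G or N) as covariates.

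The cost is a few sentences, a visit restriction and one more covariate in the code, and 1 degree of freedom per ratio model. The Day 1 samples are already planned for all subjects, so no new data are needed.
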